Appendix 4. Barthel Index

The Barthel Index (BI) is an ordinal scale used to measure performance in 10 activities of daily living. Scores range from 0 to 100, with higher scores indicating better performance in these activities. (*Source: Md State Med J. 1965 Feb;14:61-5.*)

Category	Scale definition
Feeding	0 = unable 5 = needs help cutting, spreading butter, etc., or requires modified diet 10 = independent
Bathing	0 = dependent 5 = independent (or in shower)
Grooming	0 = needs to help with personal care 5 = independent face/hair/teeth/shaving (implements provided)
Dressing	0 = dependent 5 = needs help but can do about half unaided 10 = independent (including buttons, zips, laces, etc.)
Bowels	0 = incontinent (or needs to be given enemas) 5 = occasional accident 10 = continent
Bladder	0 = incontinent, or catheterized and unable to manage alone 5 = occasional accident 10 = continent
Toilet use	0 = dependent 5 = needs some help, but can do something alone 10 = independent (on and off, dressing, wiping)
Transfers (bed to chair and back)	0 = unable, no sitting balance 5 = major help (one or two people, physical), can sit 10 = minor help (verbal or physical) 15 = independent
Mobility (on level surfaces)	0 = immobile or < 50 yards 5 = wheelchair independent, including corners, > 50 yards 10 = walks with help of one person (verbal or physical) > 50 yards 15 = independent (but may use any aid; for example, stick) > 50 yards
Stairs	0 = unable 5 = needs help (verbal, physical, carrying aid) 10 = independent

Guidelines:

1. The index should be used as a record of what a patient does, not as a record of what a patient could do.
2. The main aim is to establish degree of independence from any help, physical or verbal, however minor and for whatever reason.
3. The need for supervision renders the patient not independent.
4. A patient's performance should be established using the best available evidence. Asking the patient, friends/relatives and nurses are the usual sources, but direct observation and common sense are also important.

However, direct testing is not needed.

5. Usually the patient's performance over the preceding 24–48 hours is important, but occasionally longer periods will be relevant.

6. Middle categories imply that the patient supplies over 50 per cent of the effort.

7. Use of aids to be independent is allowed.

Appendix 5. EUROQOL 5D-5L

The EuroQoL 5-Dimension 5-Level (EQ-5D-5L) questionnaire is a standardized instrument for measuring health outcomes and is widely used in stroke patients. (*Source: Health Policy. 1990 Dec;16(3):199-208.*)

Category	Scale definition
Mobility	 I have no problems in walking about  I have slight problems in walking about  I have moderate problems in walking about  I have severe problems in walking about  I am unable to walk about
Self-care	 I have no problems washing or dressing myself  I have slight problems washing or dressing myself  I have moderate problems washing or dressing myself  I have severe problems washing or dressing myself  I am unable to wash or dress myself
Usual activities (e.g. work, study, housework, family or leisure activities)	 I have no problems doing my usual activities  I have slight problems doing my usual activities  I have moderate problems doing my usual activities  I have severe problems doing my usual activities  I am unable to do my usual activities
Pain/discomfort	 I have no pain or discomfort  I have slight pain or discomfort  I have moderate pain or discomfort  I have severe pain or discomfort  I have extreme pain or discomfort
Anxiety/depression	 I am not anxious or depressed  I am slightly anxious or depressed  I am moderately anxious or depressed  I am severely anxious or depressed  I am extremely anxious or depressed

Appendix 6. eTICI

The Expanded Thrombolysis in Cerebral Infarction (eTICI) scale is a standardized method for assessing the degree of vascular reperfusion after endovascular treatment in patients with acute ischemic stroke. It is widely used in clinical research and practice for acute ischemic stroke. (*Source: J Neurointerv Surg. 2014 Mar;6(2):83-6.*)

Score	Definition
0	No perfusion or anterograde flow beyond site of occlusion.
1	Penetration but not perfusion. Contrast penetration exists past the initial obstruction but with minimal filling of the normal territory.
2	Incomplete perfusion wherein the contrast passes the occlusion and opacifies the distal arterial bed but rate of entry or clearance from the bed is slower or incomplete when compared with non-involved territories.
2a	Some perfusion with distal branch filling of < 50% of territory visualized.
2b	Substantial perfusion with distal branch filling of > 50% of territory visualized.
2c	Near-complete perfusion except for slow flow in a few distal cortical vessels or presence of small distal cortical emboli.
3	Complete perfusion with normal filling of all distal branches.

[figure not shown]
Appendix 7. mAOL

The modified Arterial Occlusive Lesion (mAOL) scale is a standardized method used to evaluate arterial recanalization in acute ischemic stroke patients following endovascular treatment. It assesses the degree of reopening in the previously occluded artery, providing critical insights into the success of the intervention. (*Source: Stroke. 2013 Sep;44(9):2650-63.*)

Grades	Definitions
Grade 0	Complete occlusion of the target artery.
Grade 1	Incomplete occlusion or partial local recanalization at the target artery with no distal flow.
Grade 2	Incomplete occlusion or partial local recanalization at the target artery with any distal flow.
Grade 3	Complete recanalization and restoration of the target artery with any distal flow.

Appendix 8. PC-ASPECTS

The Posterior Circulation Alberta Stroke Program Early CT Score (PC-ASPECTS) is a standardized tool used to evaluate early ischemic changes in the posterior circulation territory. (*Source: Stroke. 2008 Sep;39(9):2485-90.*)

Region	Initial Points	Ischemic/Hypodense Changes Present	Subtracted Points
Left Thalamus	1	Yes	-1
Right Thalamus	1	Yes	-1
Left Cerebellum	1	Yes	-1
Right Cerebellum	1	Yes	-1
Left PCA Territory	1	Yes	-1
Right PCA Territory	1	Yes	-1
Midbrain (any part)	2	Yes	-2
Pons (any part)	2	Yes	-2

Notes:

1. Initial score is 10.
2. Subtract the specified points for each region if early ischemic changes or hypodensity are detected.
3. PC-ASPECTS = 10 indicates a normal scan (no abnormalities).
4. PC-ASPECTS = 0 indicates ischemic changes or hypodensity in all the above regions.

Appendix 9. Heidelberg Bleeding Classification (HBC)

(Source: *Stroke*. 2015 Oct;46(10):2981-6.)

Class	Type	Description
1 Hemorrhagic transformation of infarcted brain tissue		
1a	HI1	Scattered small petechiae within infarcted brain tissue, no mass effect.
1b	HI2	Confluent petechiae within the infarct area, no mass effect.
1c	PH1	Hematoma within infarcted tissue, occupying <30%, no substantive mass effect.
2 Intracerebral hemorrhage within and beyond infarcted brain tissue		
	PH2	Hematoma occupying $\geq 30\%$ of the infarcted tissue, extending within and beyond the infarcted area, with obvious mass effect.
3 Intracerebral hemorrhage outside the infarcted brain tissue or intracranial-extracerebral hemorrhage		
3a	Parenchymal hematoma remote from infarcted brain tissue	
3b	Intraventricular hemorrhage	
3c	Subarachnoid hemorrhage	
3d	Subdural hemorrhage	

Abbreviations: HBC, Heidelberg bleeding classification; HI, hemorrhagic infarction; PH, parenchymatous hematoma.

Notes:

1. Symptomatic intracranial hemorrhage: new intracranial hemorrhage detected by brain imaging associated with any of the item below:

1.1 ≥ 4 points total NIHSS at the time of diagnosis compared to immediately before worsening. Note that a 4 points change is not compared with the baseline admission NIHSS score but instead to the immediate predeterioration neurological status

1.2 ≥ 2 points in one NIHSS category. The rationale for this is to capture new hemorrhages that produce new neurological symptoms, making them clearly symptomatic but not causing worsening in the original stroke territory. For example, a new remote hemorrhage in the contralateral occipital lobe may cause new hemianopia that is clearly symptomatic but the patient will not have worsening of ≥ 4 points on the NIHSS score.

1.3 Leading to intubation/hemicraniectomy/external ventricular drain placement or other major medical/surgical intervention.

1.4 Absence of alternative explanation for deterioration 4b.

2. Asymptomatic intracranial hemorrhage: new hemorrhage that has no implications for prognosis or change in management, and there is no substantive change in the patient's neurological status.

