Appendix 10. SITS-MOST Criteria

(*Source: Lancet. 2007 Jan 27;369(9558):275-82.*)

Evaluation Dimension	Scoring Criteria
Imaging Evidence	Intracranial hemorrhage detected on CT or MRI post-treatment.
Hematoma Type	PH 2: hematoma occupies $\geq 30\%$ of the infarcted area with significant mass effect.
Neurological Deterioration	NIHSS score increased by ≥ 4 points compared to baseline or the lowest value within 24 hours, or led to death.
Overall Assessment	If all the above criteria are met, classify as symptomatic intracerebral hemorrhage.

Notes: PH 2, parenchymal haemorrhage 2.

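### Appendix 9 lists the no-other-explanation condition as one of four sufficient criteria for Heidelberg sICH, so a deterioration with another cause can be classified as symptomatic

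*Protocol*

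**What the plan says.** Protocol section 8.1.3 names intracranial haemorrhage and sICH as a safety endpoint and refers to Appendices 9 to 11 for definitions. Appendix 9, note 1, defines sICH as "new intracranial hemorrhage detected by brain imaging associated with any of the item below". Four items follow at the same level:

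- 1.1: a change of at least 4 "points total NIHSS at the time of diagnosis compared to immediately before worsening".
- 1.2: a change of at least 2 points in a single NIHSS category, with an explanatory remark: "The rationale for this is to capture new hemorrhages that produce new neurological symptoms".
- 1.3: "Leading to intubation/hemicraniectomy/external ventricular drain placement or other major medical/surgical intervention".
- 1.4: "Absence of alternative explanation for deterioration 4b".

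Note 2 defines an asymptomatic bleed as one without consequences for prognosis or management in which "there is no substantive change in the patient's neurological status". Appendix 10 (SITS-MOST) uses the opposite joining rule: "If all the above criteria are met, classify as symptomatic intracerebral hemorrhage".

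The SAP repeats the endpoint in section 2.2 without defining it. Section 3.10 compares the safety endpoints between arms with a test, a risk difference and a risk ratio.

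**The concern.** Items 1.1 to 1.3 describe something that happened to the patient. Item 1.4 describes how that event is to be attributed. It speaks of a deterioration that must already have been established, so it makes sense only as a qualifier on the other three. Placed under an any-of rule, it has two unintended effects:

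- It does not restrain 1.1. A worsening of at least 4 points caused by, say, re-occlusion or oedema, in a patient who also has an incidental petechial bleed, satisfies the definition although another cause is known.
- It bypasses the thresholds. A smaller worsening, below the limits in 1.1 and 1.2, satisfies the definition through 1.4 if no other cause is found.

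The arms differ by intravenous thrombolysis, and the incidence of sICH is among the protocol's stated objectives (section 2). What is at stake is how specific that safety endpoint is, and whether two adjudicators would classify the same patient in the same way.

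**Working it through.** No figure in the documents depends on this definition, so there is none to reproduce. The check is one of logic, followed by an illustration on assumed values.

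**1. Does each item carry its own causal link?** Item 1.1 has none: it compares two NIHSS totals. Item 1.2 shows a causal intention, but only in its rationale. Item 1.3 carries one in its opening words. Item 1.4 is the attribution condition itself. Item 1.1 is thus the most exposed.

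**2. Truth table.** Take a new bleed on imaging as given, and let each item be present or absent: 2^4 = 16 patterns.

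- As written, 1.1 OR 1.2 OR 1.3 OR 1.4: 16 − 1 = 15 patterns are sICH.
- With 1.4 required, (1.1 OR 1.2 OR 1.3) AND 1.4: (2^3 − 1) × 1 = 7 patterns are sICH.
- Difference: 15 − 7 = 8. In 7 of these, at least one of 1.1 to 1.3 is met but another explanation exists. In the remaining 1, only 1.4 is met.

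This counts logical patterns and says nothing about how often each occurs.

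**3. Is it repaired elsewhere?**

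| Place | What it adds |
|---|---|
| Protocol 8.1.3 | A pointer to Appendices 9 to 11 |
| Protocol 8.1.6 | Blinded double reading of images; medical records are mentioned only for the cause of stroke |
| Protocol 11.2.2 | sICH is evaluated by the imaging committee on CT; no attribution rule |
| SAP 2.2 and 3.10 | The endpoint and its analysis; no definition |

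None makes 1.4 a requirement. Appendix 10 shows that the protocol says so when it means all items to be met.

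**4. Size, on assumed values only.** Extra cases per arm through 1.1 to 1.3 = 170 × (share with any new bleed) × (share of those meeting 1.1, 1.2 or 1.3) × (share of those with another explanation). The 170 per arm is the protocol's figure. The three shares are assumptions, taken as 10–30%, 10–30% and 10–50%.

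- Low end: 170 × 0.10 × 0.10 × 0.10 = 0.17, about 0.2 patients per arm.
- Middle: 170 × 0.20 × 0.20 = 6.8 as written; 6.8 × 0.70 = 4.8 with 1.4 required; difference 2.0.
- High end: 170 × 0.30 × 0.30 × 0.50 = 7.65, about 7.6 patients per arm.

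Cases entering through 1.4 alone are not included.

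**5. Direction, also on assumed values.**

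- Equal additions: suppose the true rates are 8% and 4%, so the risk ratio is 2.0 and the risk difference 4 points. Adding 2 points to each arm gives 10% and 6%. The risk ratio falls to 10/6 = 1.67, while the risk difference stays at 4 points and loses some precision.
- Unequal additions: suppose any new bleed occurs in 30% of one arm and 20% of the other, with the other two shares at 20% and 30%. The extra cases are 170 × 0.30 × 0.20 × 0.30 = 3.1 and 170 × 0.20 × 0.20 × 0.30 = 2.0. The arm that bleeds more gains more false cases, and a difference could be exaggerated.

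**The case against.** The best reply is that experienced blinded adjudicators will read item 1.4 as intended. The definition speaks of association, 1.2 explains its causal purpose, 1.3 requires that the bleed led to the intervention, and the stray 4b suggests a slip in transcription. This has some force, and use of 1.4 alone to override the thresholds may be rare. But association is not attribution, a rationale is not a rule, and 1.1 contains no such hint. If adjudicators are expected to depart from the text, the text should be corrected.

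A reader might also infer stronger points, which the documents do not support:

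- *That any deterioration not due to bleeding counts as sICH.* A new bleed on imaging is always required, so only deteriorations that coincide with one can be misclassified.
- *That patients intubated for unrelated reasons are counted.* Item 1.3 requires the bleed to have led to the intubation, so these patients do not meet it even as written.
- *That a real bleeding signal from thrombolysis is masked.* Equal additions dilute the risk ratio but not the risk difference, and unequal additions could exaggerate a signal.
- *That sICH as a whole is compromised.* The endpoint also cites SITS-MOST, which requires a large parenchymal haematoma and would exclude the petechial example. ECASS II, as worded in Appendix 11, contains no attribution rule and so does not help. Neither document says which of the three definitions leads.

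**Conclusion.** The point holds as an error in a stated endpoint rule. By its text, Appendix 9 lets a bleed with a deterioration explained by something else be classified as sICH, and lets a deterioration below the thresholds qualify through 1.4 alone. That 1.4 was meant as a condition follows from its own wording and does not rest on the cited publication.

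The Heidelberg sICH endpoint is less specific than it should be. By how much is unknown: the assumed ranges give about 0.2 to 7.6 extra cases per 170-patient arm, and no rate in the documents narrows this. The direction of any effect on the comparison between arms cannot be determined either. Claims that the sICH rate is inflated by a particular amount, or that the comparison is pulled toward no difference, therefore go further than the documents allow. The primary endpoint, sample size and type I error are untouched. The correction is worth making because it is cheap and the endpoint is formally compared between arms.

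**What to change.** 1. Reword note 1 so that sICH requires a new intracranial haemorrhage on imaging, with at least one of 1.1, 1.2 or 1.3, AND no other explanation for the deterioration.
2. Delete the stray 4b.
3. Amend note 2 so that a bleed accompanied by a deterioration from another cause is classified as not symptomatic. Otherwise, once note 1 is corrected, such a patient fits neither category.
4. State that blinded adjudicators judge attribution, using the clinical records as well as the CT. Section 11.2.2 mentions only CT for sICH, so it should not be assumed that those records already reach them.

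The cost is a short edit to an appendix, some added record review in patients with a new bleed, and a check of adjudications already made against the corrected rule, blinded to allocation. No treatment, visit or sample size changes.

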Appendix 10. SITS-MOST Criteria

(*Source: Lancet. 2007 Jan 27;369(9558):275-82.*)

Evaluation Dimension	Scoring Criteria
Imaging Evidence	Intracranial hemorrhage detected on CT or MRI post-treatment.
Hematoma Type	PH 2: hematoma occupies $\geq 30\%$ of the infarcted area with significant mass effect.
Neurological Deterioration	NIHSS score increased by ≥ 4 points compared to baseline or the lowest value within 24 hours, or led to death.
Overall Assessment	If all the above criteria are met, classify as symptomatic intracerebral hemorrhage.

Notes: PH 2, parenchymal haemorrhage 2.

Appendix 11. ECASS II Classification

(Source: *Lancet*. 1998 Oct 17;352(9136):1245-51.)

Category	Definition
HI1	Small petechiae along the margins of the infarct.
HI2	Confluent petechiae within the infarcted area but no space-occupying effect.
PH1	Blood clots in 30% or less of the infarcted area with some slight space-occupying effect.
PH2	Blood clots in more than 30% of the infarcted area with substantial space-occupying effect.
Overall Assessment	Symptomatic Intracerebral Hemorrhage is classified if: blood at any site in the brain on the CT scan (as assessed by the CT reading panel, independently of the assessment by the investigator), documentation by the investigator of clinical deterioration, or adverse events indicating clinical worsening (e.g., drowsiness, increase of hemiparesis) or causing a decrease in the NIHSS score of 4 or more points.

Notes: HI 1, haemorrhagic infarction 1; HI 2, haemorrhagic infarction 2; PH 1, parenchymal haemorrhage 1; PH 2, parenchymal haemorrhage 2; sICH, symptomatic Intracranial haemorrhage.

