8.1.3 Safety endpoints

The safety endpoints include:

- (1) All-cause mortality within 7, 30±7, and 90±14 days after stroke onset.
- (2) Proportions of patients with intracranial hemorrhage and symptomatic intracranial hemorrhage (**Appendices 9–11**) at 24–72 hours after procedure and 5–7 days after stroke onset.
- (3) Proportions of patients with new regional cerebral embolisms during EVT (**Appendix 12**).
- (4) Proportions of patients with new cerebral infarction at 24–72 hours after procedure and 5–7 days after stroke onset.
- (5) EVT procedure-related complications within 90±14 days after stroke onset.
- (6) Other serious adverse events within 90±14 days after stroke onset.

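### The ECASS II rule in Appendix 11 joins bleeding and clinical worsening only by commas and *or*; it should require blood on CT together with a clinical criterion.

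*Protocol*

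**What the plan says.** Safety endpoint (2) in Protocol Section 8.1.3 is "Proportions of patients with intracranial hemorrhage and symptomatic intracranial hemorrhage" at 24–72 hours after the procedure and 5–7 days after onset. It points to Appendices 9–11 and does not say which of the three definitions governs. SAP Section 2.2 repeats the endpoint, and SAP Section 3.10 describes how safety endpoints are summarised. Neither defines symptomatic haemorrhage.

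The three definitions are:

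- **Appendix 9 (Heidelberg):** "new intracranial hemorrhage detected by brain imaging associated with any of the item below". It has a separate asymptomatic class: "new hemorrhage that has no implications for prognosis or change in management", without substantive neurological change.
- **Appendix 10 (SITS-MOST):** imaging evidence, haematoma type and neurological deterioration are listed, then "If all the above criteria are met, classify as symptomatic intracerebral hemorrhage".
- **Appendix 11 (ECASS II), Overall Assessment:** "Symptomatic Intracerebral Hemorrhage is classified if: blood at any site in the brain on the CT scan" (as read by the CT panel independently of the investigator), then "documentation by the investigator of clinical deterioration, or adverse events indicating clinical worsening" (with examples), "or causing a decrease in the NIHSS score of 4 or more points".

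**The concern.** Appendices 9 and 10 each contain words that make bleeding necessary and link it to the clinical picture. Appendix 11 has none. Its elements are separated by commas, and the only conjunction is *or*. Under the ordinary reading of such a list, each item is sufficient alone.

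The incidence of symptomatic haemorrhage is named in the secondary objectives (Protocol Section 2), and bleeding is an obvious safety question when a thrombolytic is added before EVT. The DSMB also reviews the accumulating safety data (Protocol Section 9.4). If the rule were applied or programmed as written, the ECASS II version would mix silent bleeds and non-haemorrhagic worsening with true symptomatic bleeds. A between-group difference in symptomatic bleeding would then be harder to see.

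**Working it through.** The plan gives no figure to reproduce; the question is the logic of a definition. Let A = blood on CT, B = deterioration documented by the investigator, and C = an adverse event showing worsening or meeting the NIHSS limb. All three come from Appendix 11.

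- Literal rule: A or B or C.
- Linked rule: A and (B or C).

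| A | B | C | Literal | Linked |
|---|---|---|---|---|
| 0 | 0 | 0 | no | no |
| 0 | 0 | 1 | **yes** | **no** |
| 0 | 1 | 0 | **yes** | **no** |
| 0 | 1 | 1 | **yes** | **no** |
| 1 | 0 | 0 | **yes** | **no** |
| 1 | 0 | 1 | yes | yes |
| 1 | 1 | 0 | yes | yes |
| 1 | 1 | 1 | yes | yes |

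The literal rule returns symptomatic haemorrhage in 7 of 8 combinations and the linked rule in 3 of 8. They disagree in 7 − 3 = 4: one is blood without symptoms, and three are worsening without blood. These are counts of logical cases, not of patients.

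Three example records:

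- HI1 petechiae on the 24–72 hour CT, patient unchanged: literal yes, linked no. Appendix 9 would call this asymptomatic.
- Patient becomes drowsy, no blood on CT: literal yes, linked no. Appendices 9 and 10 both exclude it, because each needs haemorrhage on imaging.
- PH2 with documented deterioration: yes under both.

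On the literal rule every bleed seen on CT is also symptomatic, so the two proportions in endpoint (2) lose their distinction for those bleeds.

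The same sentence has a second fault. Its NIHSS limb refers to a *decrease* of 4 or more points. Appendix 2 states that higher scores are worse, and Appendix 10 uses an increase of at least 4. As written, the limb describes improvement.

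**The case against.** The strongest reply is that context settles the meaning. The rule's label contains both *symptomatic* and *haemorrhage*: a patient with no blood has no haemorrhage to classify, and a silent bleed is not symptomatic. The neighbouring appendices are conjunctive, Appendix 9 has an asymptomatic class, and endpoint (2) keeps the two proportions apart. Appendix 11 itself pairs a panel-read imaging element with an investigator-documented clinical one. Imaging is read by a blinded, trained and tested committee, with two readers and a senior consensus reading (Protocol Section 8.1.6), and Section 11.2.2 assigns both haemorrhage endpoints to it. The reach is also limited: this is one of three definitions for part of one safety endpoint, and the primary endpoint is unaffected.

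Most of this stands. A reader might infer from the wording that symptomatic haemorrhage will actually be miscounted. The documents do not support that, and the linked reading is the likely one in practice. A reader might also infer that the ECASS II version would simply duplicate the any-haemorrhage endpoint. That is not right either: taken literally it would also take in worsening without blood.

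What does not stand is the idea that nothing needs correcting. Every argument above asks the reader to override the words of the rule. The SAP has no derivation to fall back on, and the reversed NIHSS direction makes it unsafe to rely on readers inferring the intent of this cell. The table shells mentioned in SAP Section 4 are not among the documents, so a correct derivation may exist there, but it cannot be assumed.

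**Conclusion.** The point holds as a drafting fault in an operative safety definition, and it should be corrected. As written, Appendix 11 admits asymptomatic haemorrhage, and deterioration without haemorrhage, as ECASS II symptomatic haemorrhage. That is out of line with Appendices 9 and 10 and with the separate proportions in endpoint (2). The conjunctive meaning is probably intended.

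The size of any effect cannot be computed, because the documents give no rates of haemorrhage or of non-haemorrhagic deterioration. A reader might infer a several-fold inflation, but any multiple only restates the rates assumed. If any haemorrhage were 10–30% and symptomatic haemorrhage 3–6% (assumptions, not document figures), silent bleeds alone would give ratios from 10/6 = 1.7 to 30/3 = 10. That range is too wide to support a claim. How often patients worsen without bleeding is likewise not stated anywhere. The conclusion rests on the logic of the text alone.

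**What to change.** Reword the Overall Assessment in Appendix 11 along these lines:

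> Symptomatic intracerebral haemorrhage requires "blood at any site in the brain on the CT scan", as assessed by the CT reading panel, AND at least one of: (i) clinical deterioration documented by the investigator; (ii) an adverse event that indicates clinical worsening or causes an NIHSS change of 4 or more points in the direction of worsening.

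This keeps CT as the modality and corrects the NIHSS direction in the same edit. In the SAP, add the derivation that is now absent: the ECASS II flag is 1 only if ICH = 1 AND a clinical criterion is met.

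The cost is one sentence in the protocol, reported to the ethics committee as an amendment under Section 13.3, and one derivation rule in the SAP. No new assessments are needed: CT readings, NIHSS scores and adverse events are already collected. If any events have already been classified under Appendix 11, confirm that the linked rule was used.

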Appendix 2. NIH Stroke Scale

The NIH Stroke Scale (NIHSS) is an ordinal scale used to assess the severity of stroke by evaluating the patient's physical condition. Scores range from 0 to 42, with higher scores indicating greater severity of ischemia. The stroke scale items should be performed sequentially as listed. After each subscale assessment, record the patient's performance in each category. Scores should not be revisited or modified. Follow the provided instructions for performing each assessment technique. The score should reflect the patient's actual performance rather than what the clinician believes the patient is capable of. Responses should be documented during the examination, and the process should be conducted promptly. Unless otherwise specified, patients should not be prompted or encouraged (e.g., repeatedly asked to make a special effort). (*Source: Stroke. 1989 Jul;20(7):864-70.*)

Instructions	Scale definition

1a. Level of consciousness (LOC): The investigator must choose a response if a full evaluation is prevented by such obstacles as an endotracheal tube, language barrier, orotracheal trauma/bandages. A 3 is scored only if the patient makes no movement (other than reflexive posturing) in response to noxious stimulation.
	
0 = Alert; keenly responsive. 1 = Not alert; but arousable by minor stimulation to obey, answer, or respond. 2 = Not alert; required repeated stimulation to attend, or is obtunded and requires strong or painful stimulation to make movements (not stereotyped). 3 = Responds only with reflex motor or autonomic effects or totally unresponsive, flaccid and are flexic.

1b. LOC Questions: The patient is asked the month and his/her age. The answer must be correct – there is not partial credit for being close. Phasic and stuporous patients who do not comprehend the questions will score 2. Patients unable to speak because of endotracheal intubation, orotracheal trauma, severe dysarthria from any cause, language barrier, or any other problem not secondary to aphasia are given a 1. It is important that only the initial answer be graded and that the examiners not “help” the patient with verbal or non-verbal clues.
	
0 = Answers both questions correctly. 1 = Answers one question correctly. 2 = Answers neither question correctly.

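### The NIHSS limb of the ECASS II definition of symptomatic haemorrhage (Protocol Appendix 11) runs the wrong way: it counts a fall of 4 or more points, which is improvement

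*Protocol*

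**What the plan says.** Safety endpoint (2) in Protocol Section 8.1.3 is the proportion of patients with intracranial haemorrhage and "symptomatic intracranial hemorrhage (Appendices 9–11"), assessed at 24–72 hours after the procedure and at 5–7 days after onset. Three definitions are thus in force: Heidelberg (Appendix 9), SITS-MOST (Appendix 10) and ECASS II (Appendix 11). None is named as primary.

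Appendix 11 starts from blood anywhere in the brain on CT and continues with a comma-separated list. The list gives "documentation by the investigator of clinical deterioration, or adverse events indicating clinical worsening (e.g., drowsiness, increase of hemiparesis"), or such events "causing a decrease in the NIHSS score of 4 or more points".

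On the direction of the scale, Appendix 2 states: "Scores range from 0 to 42, with higher scores indicating greater severity of ischemia". The two sibling definitions read as follows:

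- Appendix 10 (SITS-MOST): "NIHSS score increased by ≥ 4 points compared to baseline or the lowest value within 24 hours, or led to death".
- Appendix 9 (Heidelberg): "≥ 4 points total NIHSS at the time of diagnosis compared to immediately before worsening".

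The SAP lists sICH in Section 2.2 without defining it. Section 3.10 then applies incidence rates, exact confidence intervals, group tests, risk differences and risk ratios to all safety endpoints.

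**The concern.** A threshold in a harm definition points towards recovery. sICH is central to this trial: the arms differ by intravenous thrombolysis, and its incidence is named among the secondary objectives in Protocol Section 2. The NIHSS is scored at the 24–72 hour and 5–7 day visits (Appendix 17), the same windows as the sICH endpoint, so a 4-point rule is easy to copy into a charter or a program exactly as it stands.

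An NIHSS improvement of at least 4 points is also a secondary efficacy endpoint (Section 8.1.2, item 5). The same change in score would then count as benefit in one table and appear in a harm definition in another. Nothing in the SAP would stop a programmer from taking Appendix 11 at its word.

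**Working it through.** No sample size, power or event count is involved, so the check is a comparison of texts followed by a reading of the logic.

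**Step 1: direction.**

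| Source | NIHSS change used | Meaning on the Appendix 2 scale |
|---|---|---|
| Appendix 9 (Heidelberg) | 4 or more points, relative to the state just before worsening | worsening |
| Appendix 10 (SITS-MOST) | increase of 4 or more points | worsening |
| Appendix 11 (ECASS II) | decrease of 4 or more points | improvement |

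On a 0 to 42 scale where higher is worse, Appendix 11 is the only one of the three that is reversed. The sentence is intact. No redaction or broken table explains the word.

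**Step 2: what Appendix 11 still captures.** Take a patient with blood on CT.

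(a) The NIHSS rises by 4 or more, and the investigator documents deterioration or an adverse event indicates worsening. The patient counts as sICH through those limbs, which carry no NIHSS threshold.

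(b) The NIHSS rises by 4 or more, but neither is recorded. The NIHSS limb is not met because it asks for a fall. The patient is missed.

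(c) The NIHSS falls by 4 or more without deterioration. Grammatically, the limb needs an adverse event that caused the fall. Section 9.2.1 defines an adverse event as an untoward occurrence, so recovery alone does not clearly qualify. A rule programmed as blood on CT plus a fall of at least 4 points, without the adverse-event condition, would flag this patient.

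**Step 3: effect of correcting one word.** With *increase* in place of *decrease*, the limb would still hang on an adverse event. On a strict reading, patient (b) would still be missed. The direction and the sentence structure both need attention if the NIHSS limb is to act as an objective trigger.

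**Step 4: reach.** Appendices 9 and 10 are not reversed. The 4-point item in Appendix 9 covers patient (b) if the haemorrhage is new and the rise is measured from just before the worsening. Appendix 10 covers patient (b) only if the haematoma is also of type PH2, because all its criteria must be met.

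**The case against.** The best defence is that this is a drafting slip that no competent adjudicator would follow. The surrounding sentence is about deterioration, two of its limbs catch worsening without any score, and two of the three sICH definitions point the right way. Imaging is read by trained, blinded readers in pairs (Section 8.1.6), and there is an Independent Adverse Event Assessment Committee (Section 11.2.1). Much of this stands, and it limits the practical effect. It does not remove the error. No section corrects the word, the SAP offers no overriding definition, and different readers may repair the sentence differently.

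Two stronger readings are tempting, and the documents support neither.

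- A reader might infer that a 4-point worsening goes uncounted altogether. It does not: documented deterioration or a worsening adverse event still qualifies the patient. Only the objective trigger is lost.
- A reader might infer that bleeding in recovering patients automatically becomes symptomatic, so that the arm that improves more is charged with more sICH. That requires dropping the adverse-event condition, and no section specifies a bare NIHSS rule. Multiplying an assumed haemorrhage rate by an assumed improvement rate would also ignore that condition, and neither rate is given in the documents. A bias between arms would further need an assumed imbalance in incidental bleeding.

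**Conclusion.** Wrong as written. The NIHSS limb in Appendix 11 contradicts the protocol's own scale in Appendix 2 and the matching threshold in Appendix 10, and Section 8.1.3 makes Appendix 11 an operative definition of a safety endpoint. The demonstrable consequence is narrow. The ECASS II version of sICH loses its objective 4-point worsening criterion, so patients with a measured rise but no recorded deterioration or worsening event are missed. Flagging of improvement is a risk only if the rule is programmed literally without the adverse-event condition.

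The number of patients affected cannot be estimated from the documents. It depends on how often a 4-point rise goes undocumented and on how the adjudicators and programmers apply the sentence. The conclusion about direction rests on no assumption beyond the text of Appendices 2, 10 and 11.

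**What to change.** In Appendix 11, replace *decrease* with *increase* and write the logic explicitly:

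blood on CT AND (investigator-documented clinical deterioration OR adverse events indicating clinical worsening OR an NIHSS increase of 4 or more points).

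This keeps all the existing limbs. In particular, the limb on adverse events indicating worsening must not be lost in the rewrite. The explicit form makes the NIHSS limb stand on its own, which a change of word alone would not do. Since Appendix 11 names no reference score for the NIHSS change, whereas Appendices 9 and 10 each do, the same edit is the place to state one.

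Send the corrected text to the endpoint, imaging and adverse-event committees and to the SAP programmers. The cost is a short correction to one appendix, reported to the ethics committee as an amendment under Section 13.3, and a note to those groups. No new data are needed. Any sICH classification already made under the ECASS II definition should be rechecked against the corrected text.
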